### **Pictorial Representation of Illness and Self-Measure (PRISM)**

The burden of suffering can be evaluated by using PRISM (Pictorial Representation of Illness and Self-Measure), which is a brief quantitative method to assess the perceived burden of suffering due to illness [68]. The PRISM tool consists of an A4-size paperboard, which stands for the patient's life and a yellow disk, representing the patient, is fixed at the bottom right-hand corner. The patient is asked to reflect the importance of the illness in his/her life by placing a red disk, which represents his/her illness, on the metal board. Thereby, the PRISM tool provides a graphic representation of the patient's illness in relation to the patient. Validity and reliability of the PRISM tool were assessed with over 700 patients with a variety of chronic physical illnesses (including RA, SLE, OA, DM II and COPD) and has been shown to strongly correlate with psychological variables and with SF-36 subscale scores.

PRISM will be presented in a cardboard version and should require approximately 2 minutes to complete (Annex 3).

### **Patient Activation Measure – (PAM-13)**

Patient Activation refers to people's ability and willingness to take on the role of managing their health and health care [69]. The concept of activation focuses on skills and knowledge required for day-to-day management of one's own health [69]. Positive changes in patient activation can lead to positive self-management behaviour changes in patients with chronic conditions [70].

Patient activation interventions have been developed for patients with cancer, diabetes, hypertension, obstetrical and gynaecological issues, and end-stage renal disease [71]. Such interventions work to increase patient involvement in personal healthcare through education and skill-building, often targeted toward patients initiating specific conversations with their clinicians, thereby promoting a bidirectional interaction between clinicians and patients [72].

#### **The Patient Activation Measure**

The Patient Activation Measure (PAM) is a tool for measuring the level of patient engagement in their healthcare. It was designed to assess an individual's knowledge, skill and confidence for self-management [73]. PAM was developed by Hibbard and colleagues in 2004 originally as a 22 item scale, the PAM 22, and subsequently as a 13 item short form [74] [75]. The PAM's 13-item scale asks people about their beliefs, knowledge and confidence for engaging in a wide range of health behaviours and then assigns an activation score based on their responses to the 13-item scale. The PAM was formulated in two versions targeted at people with or without chronic disease, with few reported semantic differences. The authors also report that the measure has good psychometric properties indicating that it can be used at the individual patient level to tailor interventions and assess changes. Hibbard and colleagues [74] identified four elements; knowledge, skills, confidence and behaviours critical for coping with a chronic illness, and suggested four stages of activation that patients go through on their way to becoming fully activated in managing their own health. The PAM 13 questionnaire should require approximately 7 minutes to complete and is presented in Annex 4.

#### **Patient Support Program (PSP) Questionnaire**

The PSP utilization and satisfaction assessment will evaluate the frequency of utilization and patient's overall satisfaction with the Patient Support Program "AbbVie Care".

---

Confidential Information

AbbVie Care is a free-of-charge, comprehensive multilingual patient support program, designed to accompany HCV patients under AbbVie HCV medication throughout their treatment. The service includes a wide set of education materials (in German, Russian and Turkish), automated reminder messages, a free service hotline (Mon-Sun, 8am - 10pm), a personal telephone coach as well as online resources ([www.abbvie-care.de](http://www.abbvie-care.de)).

The PSP questionnaire should require approximately 2-5 minutes to complete and is presented in Annex 5-6.

PRO data are not considered a potential source of adverse reactions. However, participating sites should review the PRO data and if a possible product-related event (including a suspected adverse reaction) is noted, the health care provider (HCP) must determine whether the event is related to Paritaprevir/r – Ombitasvir ± Dasabuvir (or any other AbbVie authorized product) and if so, it should be reported to AbbVie. The relevant AbbVie Pharmacovigilance contact details are specified in Section 11.0.

## 9.5 Study Size

In studies investigating the interferon-free ABBVIE REGIMEN ± RBV, SVR12 rates of about 95% were observed, even in difficult-to-treat CHC patients (e.g. cirrhotic G1a treatment experienced patients). To describe in routine clinical practice the effectiveness of the ABBVIE REGIMEN ± RBV in patients with CHC a precise estimate of the SVR12 rates in the core population of this study should be achieved (see Section 9.7.1 for the definition of the core population).

It is expected, that during the planned recruitment period of 12 months about 650 patients with ABBVIE REGIMEN ± RBV can be included into this observational study, and that at least 620 patients will be evaluable in the core population. As obvious from.

Table 3, if the SVR12 rate is at least 95%, then with 620 patients the width of the 95% confidence interval (CI) will not be wider than 3.5%. Even in the case that fewer patients will be enrolled and only 590 patients can be evaluated in the core population, the 95% CI will have a width of ≤3.6% for a SVR12 rate of 95%.

### Table 3 Width of 95% Confidence Interval for SVR12

---

Confidential Information

Number of patients	SVR12 rates	95% Confidence Interval*		
		Lower Limit	Upper Limit	Width
620	95%	93.0	96.5	3.5%
590	95%	92.9	96.5	3.6%
62	95%	86.5	98.3	11.8%

\* exact two-sided 95% confidence interval according to Wilson's Score method

Assuming, that in total 620 patients will be evaluable, and subgroups of interest consist of at least 10% of the entire group (i.e. ≥62 patients), then the width of the 95% CI will be <12% for a SVR12 rate of 95%, which is also considered sufficiently precise for subgroup analyses.

## 9.6 Data Management

### 9.6.1 Electronic Case Report Forms

Data for this study will be recorded by each participating center via an electronic data capture (EDC) system using a web-based eCRF from the company AMEDON, located in Lübeck, Germany. The eCRF software from AMEDON is server based and accessed by users via the internet. The users only need an internet browser. AMEDON's eCRF was confirmed to meet existing regulatory requirements for eCRFs and be compliant with the stipulations laid down in 21 CFR Part 11.

The eCRF is a closed application. Only registered users are granted access. Data entered are exclusively stored on the central server. There are no data backed up on the computer of the user. An audit trail documents each episode of an access or a transaction in the eCRF. Data are transmitted 128-bit encrypted (SSL & MD5). The database is protected by a firewall, by SSL-Certificate and SSH (Secure Shell). A backup of the stored data is being run every 24 h.

Access to the AMEDON computer center is securely protected by two barriers with owning based access control and additionally one with knowledge based access control. Visitors can only access the computer center with attendance of at least one employee of the computer center. All visits are logged with name and time.

To ensure confidentiality of data during maintenance of software or equipment, it is ensured that servers can only be accessed from separate computers in the AMEDON office. Technicians of the computer center have no access to the database. Study data are replicated on at least two storage areas in different rooms.

---

#### Confidential Information

No use or disclose outside AbbVie is permitted without prior written authorization from AbbVie  
 Version 3.0. (22. Apr 2015) – Germany V3.0 (17. November 2016)

Page 34 of 63

Access to the EDC system will be provided for the duration of the study through a password-protected method of internet access. To obtain a user account for the eCRF application of a project, the user has to contact the data management Support Team. Each user receives his/her individual user account with user name and password to his/her personal email address only. After the registration, the user receives an email with the personal details. The email contains the user name, password and the link to the application. Each user has an own access to the productive eCRF (group accounts are not accepted). For identity protection, it is not allowed that users pass on their access codes to other persons. All actions of a user are assigned to a user within the database. Confirmed actions are considered to be the electronic equivalent of a user's signature, and are therefore saved in the data base.

Examinations, diagnostic measures, laboratory assessments, findings and observations routinely performed in patients with CHC included in this cohort, will be transcribed by the investigator or designee from the source documents into the eCRF. Only data specified in the protocol will be entered into the eCRF. For each enrolled patient, the investigator or designee will create a new patient file in the eCRF and a unique patient number will be automatically allocated by the system.

If a patient withdraws Informed Consent, data documentation is immediately stopped. Study data obtained up to the date Informed Consent has been withdrawn can be used for analyses if not explicitly revoked by patient. If use of the data has been explicitly revoked by patient, data will be deleted from the eCRF (but still remains in the audit trail for regulatory purposes).

A comprehensive data validation program utilizing front-end checks in the eCRF will validate the data. Automated checks for data consistency will be implemented; discrepancies need to be solved by the researcher in the eCRF before the module can be completed.

Follow-up on eCRF data for medical plausibility will be done by AbbVie personnel (or their representatives). Queries will be generated in the eCRF for online resolution at the site. The investigator or an authorized member of the investigator's staff will make any necessary data corrections to the eCRF. All change information, including the date and person performing the corrections, will be available via the audit trail, which is part of the EDC system.

The principal investigator of each site will finally review the eCRFs for completeness and accuracy of available data and provide his or her electronic signature and date to the eCRFs as evidence thereof.

---

**Confidential Information**

At the end of the study and database closure, AMEDON will uninstall the eCRF application and delete all data in the database as per their SOPs. Prior to that, data will be provided to the responsible statistician for analyses. In addition, eCRF data (PDF-files) of patients enrolled at specific sites will be made available to the sites for archiving at study end (e.g. via CD). The complete set of eCRF data will be passed to the sponsor and archived in the pertinent sponsor repository for 10 years. After this period, data will be deleted/destroyed as per AbbVie SOPs.

Whereas eCRF data are hosted on AMEDON servers, study questionnaire data are located on IST servers in a protected and access-restricted environment. Original Questionnaires will be sent from the participating site to:

IST GmbH  
[name]  
[name]  
Germany

For information on publishing of study data, please refer to section 12 ('Plans for Disseminating and Communicating Study Results').

### **9.6.2 Assignment of Preferred Terms**

AEs will be coded using the Medical Dictionary for Regulatory Activities (MedDRA) and will be tabulated by primary MedDRA system organ class (SOC) and preferred term (PT). For treatments, surgical and medical procedures the international non-proprietary name (INN) Drug Terms and Procedures Dictionary will be used.

## 9.7 Data Analysis

### 9.7.1 Analysis Population, Time Windows and Handling of Missing Data

The target population (TP) is defined as all patients who fulfill the criteria specified in Section 9.2.1. The core population (CP) is defined as all patients of the TP, who have started the treatment combination recommended in the current local label for their disease characteristics. Patients not receiving the treatment recommended in the local label will be summarized in the non-core population (NCP). In addition, the core population with sufficient follow-up data (CPSFU) is defined as all CP patients, who fulfil one of the following criteria:

- (1) evaluable HCV RNA data  $\geq 70$  days after the last actual dose of the ABBVIE REGIMEN (i.e. data within the SVR12 time window)
- (2) a HCV RNA value  $\geq 50$  IU/mL at the last measurement post-baseline (i.e. no virological response achieved at the last measurement on-treatment or post-treatment)
- (3) HCV RNA  $< 50$  IU/mL at the last measurement post-baseline, but no HCV RNA measurement  $\geq 70$  days after the last actual dose of the ABBVIE REGIMEN due to reasons related to safety (e.g. dropped out due to AE) or incomplete efficacy information (e.g. virologic failure such as relapse is reported in the eCRF but date and value of the corresponding HCV RNA test is missing). This means only patients who had virological response at their last on-treatment or post-treatment measurement, but had no HCV RNA measurements  $\geq 70$  days post-treatment for reasons not related to safety or effectiveness (e.g. lost-to-follow-up or patient not willing to perform an additional HCV RNA test  $\geq 70$  days post-treatment) will be excluded from this analysis.

The Safety Population (SP) is defined as all patients who received at least one dose of the ABBVIE REGIMEN.

In accordance with the non-interventional nature of the study all HCV RNA measurements will be performed at the sole discretion of the physician and all HCV RNA measurements have to be entered into the eCRF. All recorded HCV RNA values will be assigned to appropriate time points (baseline, on-treatment visits, EoT visit, post-treatment visits). The time windows for the assignments will be specified in the statistical analysis plan (SAP).

No data will be imputed for any effectiveness or safety analyses except for the analyses of the HCV RNA endpoints. When there is no HCV RNA value in a visit time window post-baseline, but prior to EoT, the closest values before and after the window, regardless of the value chosen for the subsequent and preceding window, will be used for the flanking imputation described below. If a patient has a missing HCV RNA value at a post-baseline visit prior to EoT but has undetectable HCV RNA (with LLoD  $\leq 50$  IU/mL) or unquantifiable, but detectable HCV RNA levels (with LLoQ  $\leq 50$  IU/mL) at both the preceding and succeeding measurements, the HCV RNA level will be considered undetectable or unquantifiable, respectively, at this visit for this patient. In addition, if a patient has an unquantifiable HCV RNA level at the preceding measurement and an undetectable HCV RNA level at the succeeding measurement, or vice versa, the HCV RNA level will be imputed as unquantifiable at this visit for this patient. For virological response at EoT a corresponding backward imputation approach will be applied. This means if HCV RNA is missing at EoT, then unquantifiable or undetectable will be assumed for EoT, if the succeeding HCV RNA value is undetectable or unquantifiable. For SVR12 the single last available HCV RNA measurement  $\geq 70$  days post-treatment will be used. Subsequent to this flanking and backward imputation, if the HCV RNA value remains missing at a specific time point, then the patients will be considered as virological failure at this time point (i.e. not undetectable or unquantifiable).

### 9.7.2 Demographics and Disease Characteristics

All baseline and disease characteristics will be summarized for the CP stratified by the CP analysis groups (i.e. based on genotype 1 subtype, fibrosis status, treatment experienced or naïve), which are relevant for scheduled treatment combination (ABBVIE REGIMEN  $\pm$  RBV) and duration (12 and 24 weeks). In addition, baseline summaries will be repeated for the SP and the TP without stratification into subgroups. Summary statistics (n, mean, median, standard deviation [SD], and range) will be generated for continuous variables (e.g. age and body mass index [BMI]). The number and percentage of patients will be presented for categorical variables (e.g. gender and race). Further details of analysis populations and the CP analysis groups will be specified in the SAP, taking into account the ABBVIE REGIMEN recommended in the current local label for various patient groups.

### 9.7.3 Effectiveness Analysis

The primary effectiveness analysis on clinical outcomes will be performed on all patients in the CP stratified by the CP analysis groups. Due to the non-interventional nature of this study several different methods for determination of the HCV RNA value can be applied. For the purpose of the statistical analysis, a HCV RNA measurement is considered  $\leq 50$  IU/mL,

- if a PCR test was used
- and the test result is undetectable and the LLoD of the test is  $\leq 50$  IU/mL or the test result is unquantifiable and the LLoQ is  $\leq 50$  IU/mL

#### 9.7.3.1 Primary Effectiveness Endpoint

The percentage of patients achieving SVR12 (single last HCV RNA  $< 50$  IU/mL 12 weeks [i.e. at least 70 days] after the last actual dose of the ABBVIE REGIMEN) is the primary effectiveness endpoint.

#### 9.7.3.2 Secondary Effectiveness Endpoints

The secondary effectiveness endpoints are:

- The percentage of patients with virological response (HCV RNA  $< 50$  IU/mL) at EoT
- The percentage of patients with relapse (defined as HCV RNA  $< 50$  IU/mL at EoT followed by HCV RNA  $\geq 50$  IU/mL)
- The percentage of patients with breakthrough (defined as at least one documented HCV RNA  $< 50$  IU/mL followed by HCV RNA  $\geq 50$  IU/mL during treatment).
- The number and percentage of patients meeting each and any of the following SVR12 non-response categories:
  - On-treatment virologic failure (breakthrough [defined as above ] or failure to suppress [each measured on-treatment HCV RNA value  $\geq 50$  IU/mL])
  - Relapse (defined as HCV RNA  $< 50$  IU/mL at EoT or at the last on-treatment HCV RNA measurement followed by HCV RNA  $\geq 50$  IU/mL post-treatment)

---

Confidential Information

- Premature study drug discontinuation with no on-treatment virologic failure
- Missing SVR12 data and/or none of the above criteria

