### **9.9 Limitations of the Research Methods**

The limitations of observational studies, such as uncontrolled confounding by lack of randomization, and difficulties to clearly interpret treatment effects in the context of missing data are well known. Their validity can be increased by accurate outcome measurements, documentation of the most common confounders, sufficient length of follow-up and by activities to obtain complete recording of available data as well as by searches for missing key data.

The most important outcome measure in this study is HCV RNA. Missing or unrecorded follow-up HCV RNA data can in particular lead to an underestimation of the real SVR rate as compared to the SVR rate of interventional trials. Highly sensitive and quantitative diagnostic tests are required to measure HCV RNA levels in blood. In an observational study each center will be using its own test – either commercially available or so-called “home-brew” tests – which might change from one visit to the next within a patient data set. The challenge is to accurately and consistently document test properties such as the LLoD and the ILLoQ to put the results into perspective of prior outcomes from

randomized controlled trials with (usually) central laboratory assessments for all trial participants.

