##### 4.2.7.2 Secondary Variables

###### 4.2.7.2.1 Secondary Effectiveness Variables

###### Response

For the other response rates (i.e. RVR, SVR24 , SVR48, EoT response rate, relapse rate, viral breakthrough), the simple percentage of patients and a two-sided 95% confidence interval (CI) of the percentage will be computed (based on the Wilson's score method) as well. The RVR and EoT response rates will be reported for CP and the SVR24 and SVR48 rates will be reported for the respective CPSFU, stratified by genotype and cirrhosis status and overall. The relapse rates will be estimated stratified by SVR window (i.e. during SVR12 window=relapse12, during SVR24

window=relapse24, after SVR24 window=relapselate) and stratified by genotype and cirrhosis status and overall in patients of the CP with EoT response who fulfilled the following criteria:

- completed treatment as defined previously,
- had at least one HCV RNA measurement  $\geq 70$  days post-treatment or was a treatment failure between EoT and 70 days post-treatment.

Viral breakthrough rates [defined as at least one documented HCV RNA  $<50$  IU/mL followed by HCV RNA  $\geq 50$  IU/mL during treatment] will be estimated overall and stratified by genotype and cirrhosis status in all patients of the CP, who have at least one undetectable or unquantifiable, on-treatment HCV RNA measurement and at least one on-treatment or EoT measurement thereafter.

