### **Non-Response**

In another table, the numbers and the percentages of the SVR12 non-responder categories and responder will be summarized for CP patients, overall and stratified by genotype and cirrhosis status. The following SVR12 non-response categories will be considered:

- On-treatment virologic failure (breakthrough [defined as at least one documented HCV RNA  $<50$  IU/mL followed by HCV RNA  $\geq 50$  IU/mL during treatment] or failure to suppress [each measured on-treatment HCV RNA value  $\geq 50$  IU/mL])
- Relapse (defined as HCV RNA  $<50$  IU/mL at EoT followed by HCV RNA  $\geq 50$  IU/mL post-treatment and completed treatment as defined previously)
- Death and none of the above
- Premature study drug discontinuation with no on-treatment virologic failure and none of the above
- Insufficient virological response, other than those mentioned above (patients for whom insufficient virological response was reported, or who had HCV RNA  $\geq 50$  IU/mL post EoT) and none of the above
- Missing SVR12 data and/or none of the above criteria

Virological response rates and non-response categories will be displayed for patients who completed treatment with ABBVIE regimen, as well.

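### The stand-alone breakthrough and relapse rates count a single unconfirmed HCV RNA value of 50 IU/mL or more, so a patient who is below 50 at the next test can be counted as an event and also as an SVR12 responder.

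*Protocol*

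**What the plan says.** Protocol 9.7.3.2 defines two stand-alone event rates. The first is "The percentage of patients with breakthrough (defined as at least one documented HCV RNA" below 50 IU/mL, followed by a value of 50 or more on treatment. The second is "The percentage of patients with relapse (defined as HCV RNA" below 50 at EoT and 50 or more afterwards. The same section makes breakthrough part of the first non-response category: "On-treatment virologic failure (breakthrough [defined as above ] or failure to suppress [each measured on-treatment HCV RNA value" is 50 IU/mL or more.

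The SAP repeats the breakthrough rule in 4.2.7.2.1, under Response ("Viral breakthrough rates [defined as at least one documented HCV RNA" below 50, then 50 or more) and under Non-Response ("On-treatment virologic failure (breakthrough [defined as at least one documented HCV RNA" below 50, then 50 or more). It restricts relapse to patients who completed treatment and splits the relapse rate by SVR window. It does not ask for a second value.

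SVR12 is decided differently. Protocol 9.7.1 says "For SVR12 the single last available HCV RNA measurement" at least 70 days after treatment is used. SAP 4.1.1 uses a value at 70 to 126 days. Neither document lets an earlier breakthrough or relapse disqualify a responder.

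On the data, Protocol 9.7.1 says "all HCV RNA measurements have to be entered into the eCRF". Protocol 9.9 says that each centre uses its own test, "which might change from one visit to the next within a patient data set".

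**The concern.** Both event definitions stop at the first value of 50 or more and never look at the measurement after it. With local assays that can differ between visits, isolated discordant values are more likely than with a central laboratory, and every one of them will be in the database. Elsewhere the plan does look at neighbouring or later values: missing results are imputed from the results on either side, and the protocol decides SVR12 by the last value. No reason is given for treating breakthrough and relapse differently.

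Three things are at stake: the level of two rates that are expected to be low, the agreement between these rates and the SVR12 result, and the division of true non-responders into on-treatment failure and other causes.

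**Working it through.** **The plan's own figure.** Table 3 of the protocol (Table 1 of the SAP) gives the Wilson 95% interval for an SVR12 rate of 95% in 620 patients as 93.0 to 96.5, width 3.5%. The formula is: centre = (p + z²/2n)/(1 + z²/n); half-width = z·√(p(1−p)/n + z²/4n²)/(1 + z²/n). With p = 0.95, n = 620 and z = 1.96 it gives 92.99 to 96.46, width 3.47. The rows for 590 (92.93 to 96.49, width 3.55) and 62 (86.49 to 98.26, width 11.77) also match after rounding. None of these figures depends on the breakthrough or relapse rule.

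**Applying the written rules to three series (IU/mL).**

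1. On treatment <50, ≥50, <50, then <50 at day 84 after treatment. Breakthrough: yes. SVR12: yes.
2. EoT <50, day 30 ≥50, day 84 <50. Relapse by the protocol definition: yes. SVR12: yes. The SAP relapse strata begin with the SVR12 window, so it is unclear where this patient would appear in the SAP relapse table.
3. EoT <50, day 75 ≥50, day 120 <50. Relapse within the SVR12 window: yes. SVR12: yes by the last value.

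The breakthrough and relapse rates are computed in all qualifying core-population patients (Protocol 9.7.3.3; SAP 4.2.7.2.1), not only in non-responders, so nothing removes the overlap.

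**The non-response table.** Take a non-responder who completed treatment, had one isolated on-treatment value, was below 50 at EoT and then relapsed. This patient meets both on-treatment failure and relapse. In the SAP list, the condition that no earlier category applies starts only at death. List order is therefore the only guide between the first two, and on-treatment failure stands first. A non-responder with such a value who stopped treatment early cannot enter the discontinuation category at all, because that category requires no on-treatment failure.

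**How many later tests.** The design sections give five visits plus two interim windows for 12 weeks of treatment, and three for 24 weeks. Protocol Annexes 5 and 6 name these windows as early on-treatment and early post-treatment, plus mid-treatment for 24 weeks only. After a first negative at the early visit, about one scheduled test (EoT) remains for 12-week patients and two for 24-week patients.

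**Size.** Let f be the chance that a test gives an isolated value of 50 or more (assumed 0.1% to 0.5%; the documents give no figure). Let k be the number of later tests, treated as independent. Expected patients with at least one such value = N × (1 − (1 − f)^k).

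| N | f | k | Patients |
|---|---|---|---|
| 620 | 0.001 | 1 | 0.62 |
| 620 | 0.001 | 2 | 1.24 |
| 620 | 0.005 | 1 | 3.10 |
| 620 | 0.005 | 2 | 6.18 |

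Restricted to the 589 responders expected at 95% (0.95 × 620), the range is 589 × 0.001 = 0.6 to 589 × 0.009975 = 5.9. Non-responders expected: 620 − 589 = 31. The figure of 620 is an upper limit, because the breakthrough denominator requires an earlier negative value and a later on-treatment or EoT value.

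**The case against.** The strongest reply is that event rates and SVR12 are different endpoints, so a patient may appear under both without contradiction. The protocol itself lists relapse or reinfection after SVR12 as a secondary variable. This stands for relapse after the SVR12 window, which is legitimate in a responder. It does not cover a value that is back below 50 at the next test, on treatment or before SVR12 is decided.

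A reader might infer that the non-response table itself will label SVR12 responders as virologic failures. The documents do not support that. The categories are headed as SVR12 non-response categories, and the SAP shows responders beside them, which most naturally excludes responders. What is missing is an explicit statement that responder status is settled first.

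A reader might also infer that isolated values will dominate the reported breakthroughs. Assuming 3 to 6 true breakthroughs and two to three later tests, the share runs from 1.24/(1.24 + 6) = 17% to 9.25/(9.25 + 3) = 76%. The documents give no number of true breakthroughs, three later on-treatment tests exceed the documented schedule, and 620 is not the denominator. That share should not be used.

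There is some mitigation: detectable but unquantifiable results count as below 50 when the quantification limit is at most 50, and assay variation is disclosed as a limitation. The rates are also descriptive and secondary. These points reduce the weight of the problem but do not supply a rule. Finally, both rates were already tabulated at the third and fourth interim analyses, so any new definition comes after data were seen. That is a real cost and must be disclosed.

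**Conclusion.** The point holds for the stand-alone breakthrough rate and for relapse up to or within the SVR12 window: followed exactly, the plan can count one patient as an event and as an SVR12 responder. It also holds for non-responders with an isolated on-treatment value, who meet the first-listed failure category whatever happened later. The primary SVR12 estimate and its interval do not change.

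On the stated assumptions, about 0.6 to 6 patients (0.1% to 1.0% of 620) would have an isolated on-treatment or EoT value. That is small in absolute terms but not negligible beside about 31 expected non-responders. The overlap follows from the definitions alone; its frequency rests on an assumed rate of isolated values. This is a worthwhile correction to secondary definitions that uses data already required.

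**What to change.** In Protocol 9.7.3.2 and SAP 4.1.2 and 4.2.7.2.1:

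- Count a value of 50 IU/mL or more as breakthrough or relapse only if the next available HCV RNA value is also 50 or more, or if no later value exists. Take the next value from any phase, but before any new HCV therapy. A rule confined to one phase would still count an isolated EoT value followed by post-treatment values below 50.
- Show patients whose next value is below 50 on a separate line, such as *isolated value ≥50, not confirmed*. The count under the present rule, as used at the third and fourth interim analyses, can then still be read off.
- State that the non-response categories apply only to patients without SVR12, and assign them in a fixed hierarchy.

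The cost is SAP wording and one extra row in each of the breakthrough, relapse and non-response tables, with no new tests. There are three drawbacks. A true transient breakthrough that is re-suppressed moves to the separate line. Whether a value can be confirmed depends on how often a site tests. The definition also changes after interim tabulations, and the report must say so.
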